Vector shedding analysis by PCR and infectivity (CL)		X	X*	Weekly, as needed # Or every 2 weeks past Week 20 Home health/mobile phlebotomy services allowed From Week 34, monthly collection is allowed in the absence of home health/mobile phlebotomy services at a site or country					
 • #Collect plasma, PBMC, saliva, semen, and urine specimens at baseline and every week after study intervention until 3 consecutive specimens test negative for the given specimen type. • #Collection of blood to prepare PBMCs and assess shedding postinfusion will start from Week 20. • Semen samples may be collected at home the night before a clinic or home health/mobile phlebotomy services visit and stored in the participant's freezer until the clinic or home health/mobile phlebotomy services visit. • *Optional vector shedding sub-study (12 participants): additional samples (plasma, PBMC, saliva, semen and urine) will be collected, onsite only, 2 h [± 30 min], 24 h [± 3 h], and 72 h [± 4 h] after completion of the study intervention infusion/IV line flush. • Infectivity will be performed as applicable. Refer to Section 8.5.1 for additional details. 		

Procedures Year 1	Screening Period	Baseline Period	Study Intervention	Week 1-12 (±2 days)	Weeks 13-52 (±1 week)	
 ○ [#] The schedule of assessments should be based on Day 1. ○ *Visit 4/Week 1: The participant is not required to appear onsite. If onsite visit: perform all procedures as specified in the SoA. If not onsite visit: collect only all required laboratory specimens as specified in the SoA. ○ **Day 1: after end of study intervention infusion, 24 h hospitalization is planned. ○ Home health/mobile phlebotomy services may be used for pre-dose LFT blood draw and any time after Study Day 1/Visit 3, as needed (for most biological samples collection). ○ Clinical decisions may be based on local or central laboratory assessments. ○ Refer also to the General Notes at the beginning of the SoA.
Any additional safety tests	Ongoing (as needed)			Additional laboratory testing or procedures may be conducted as deemed clinically necessary by the investigator to ensure the safety of participants.		
Adverse events	Ongoing (including unscheduled visits)			During the short-term monitoring period (up to and including 104 weeks postinfusion) all SAEs and AEs will be collected (Section 8.3.1 and Appendix 3).		

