Vector shedding analysis by PCR and infectivity (CL)	
Every 2 weeks [#] Home health/mobile phlebotomy services allowed.
 
From Week 34, monthly collection is allowed in the absence of home health/mobile phlebotomy services at a site or country
			
 • #Collect plasma, PBMC, saliva, semen, and urine specimens every 2 weeks until 3 consecutive negative test results for the given specimen type. • Semen samples can be collected at home the night before a clinic or home health/mobile phlebotomy services visit and stored in the participant's freezer until the clinic or home health/mobile phlebotomy services visit. • Infectivity will be performed as applicable. Refer to Section 8.5.1 for additional details. 	
Any additional safety tests	Ongoing			Additional laboratory testing or procedures may be conducted as deemed clinically necessary by the investigator to ensure safety of participants.	
Adverse events	Ongoing (including unscheduled visits)			
During the short-term monitoring period (up to and including 104 weeks postinfusion) all SAEs and AEs will be collected (Section 8.3.1 and Appendix 3).
 
During the long-term monitoring period (Week 105 postinfusion to EOS) the following adverse events will be collected:
 
 • SAEs (including medically important events, Appendix 3). 	

Procedures Year 2 to Year 5	Week 53- 104 (\pm 2 weeks)	Week 105-208- (\pm 3 weeks)	EOS or Early Discontinuation Week 260 (\pm 3 weeks)	
  Home health/mobile phlebotomy services may be used as needed (for most biological samples collection only).  Clinical decisions may be based on local or central laboratory assessments. 	
Study Visit	14	15	16	17	18
Weeks after study intervention	78	104	156	208	260
					
 • Nonserious AEs determined to be related to study intervention by the investigator or where causality is unknown. 
Particular attention will be given to renal disease, autoimmune, neurological and hematological changes.

Concomitant medications and procedures	Ongoing (including unscheduled visits)				
Record concomitant therapy (related to reportable events) through the EOS (see Section 6.5).
 
All procedures and surgeries (including elective surgeries) will be recorded.
 
Note: FVIII product infusions will be recorded in the eDiary.

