
 ● To evaluate vector shedding and infectivity in body fluids. 	Vector shedding and infectivity of PF-07055480 in plasma, saliva, peripheral blood mononuclear cells (PBMC), urine, and semen until negative on 3 consecutive occasions for each specimen type.

Objectives	Endpoints

 • To evaluate exploratory pharmacodynamic biomarkers. 	
 • FVIII antigen levels. • Von Willebrand factor.

 • To compare joint health post PF-07055480 infusion to baseline and evaluate long-term joint outcomes. 	
 • Number of target joints. • Joint status as assessed by X-ray. • Joint status as assessed by ultrasound.

 • To evaluate for any effects on coagulation. 	
 • Coagulation activation tests: activated partial thromboplastin time (aPTT), international normalized ratio (INR), D-dimer, thrombin generation assay (TGA), and thrombin antithrombin level (TAT). • Comparison of FVIII activity between one stage assay and chromogenic assay. • Recovery of FVIII products post gene therapy.

 • To further compare PF-07055480 on PROs addressing health-related quality of life, activities of daily living and general health status. 	
The following PRO instruments will be compared with FVIII replacement regimen, using comparisons pre and postinfusion of PF-07055480 through 12 months and annually during the follow-up period:
 
 • Hemophilia Life Impacts Questionnaire (HLIQ). • EuroQol, 5 dimensions, 5 levels (EQ-5D-5L).

 • To further evaluate PF-07055480 mechanism of action and immune responses. 	
 • Cellular immunity by cell-mediated assays. • Binding immunoglobulin G (IgG) versus immunoglobulin M (IgM) assay. • Other biomarkers as inflammatory cytokines.

 • To evaluate the cross reactivity between AAV serotypes. 	nAbs against other AAV serotypes.
Optional liver biopsy substudy only: 
 • To evaluate vector integration in the liver 	
 • For the integrations analyses (as feasible): the number and location of integration sites, the location of the integration sites relative to transcription start sites, the nature of the

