6.3.2. Vector Shedding and Infectivity

Descriptive summaries of shedding vector levels in PBMC, saliva, urine, semen, and plasma will be provided, including a summary of peak vector levels, time to peak vector levels and time to undetectable/negative vector. Vector levels that are reported as below the lower limit of quantification (<LLoQ) by the bioanalytical laboratory are considered as negative. A peak level is defined for each participant as the highest vector level collected prior to the first set of 3 consecutive negative results in a given specimen type. If multiple assessments are collected for a study visit, the highest value will be included in the summary as a conservative approach. Number and percentage of participants who achieved 3 consecutive negative results will be reported for each specimen. Number and percentage of participants <LLoQ at each visit will also be summarized in the table.

The following time to event endpoints will be derived using the first set of three consecutive negative results in a given specimen type. Time to undetectable/negative vector (defined as time to first of three consecutive negative results), time to last of three consecutive negative results, and time to the last positive prior to three consecutive negatives will be summarized. The number of participants (n), mean, median, standard deviation, Q1, Q3, min, and max will be presented by visit in summary tables. A median plot of vector shedding over time will be generated with specimen types differentiated by different color/symbols. A box and whisker plot of vector levels over time will be generated for each specimen.

The summary table will be generated for the 'Vector Shedding Substudy' population (described in [Section 3.3.2](#)) and the 'Dosed' population. 'Vector Shedding' subgroup (optional substudy) will have more extensive vector shedding analysis performed on their specimens to further characterize the kinetics of vector shedding. The data of this subgroup will be separately presented.

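### By-visit shedding summaries have no rule for participants whose sampling ended because they cleared, so at later visits they understate clearance and overstate vector levels

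*SAP*

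**What the plan says.** **Collection stops on the outcome.** In the Year 1 table of Protocol 1.3 (Schedule of Activities), specimens are taken "every week after study intervention until 3 consecutive specimens test negative for the given specimen type". The table for Years 2 to 5 says "every 2 weeks until 3 consecutive negative test results for the given specimen type". The endpoint in SAP 2.2 has the same limit: shedding is followed "until negative on 3 consecutive occasions for each specimen type". The Year 1 table and Protocol 8.5.1 allow two-weekly collection after Week 20. From Week 34 they allow roughly monthly collection where home health services are lacking.

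**Displays run by visit.** SAP 6.3.2 plans four outputs over time:
- the percentage negative, in these words: "Number and percentage of participants <LLoQ at each visit will also be summarized in the table"
- descriptive statistics of vector level at each visit (count, mean, spread, quartiles and range)
- one figure of medians covering all specimen types: "A median plot of vector shedding over time will be generated with specimen types differentiated by different color/symbols"
- box plots of level against time, one per specimen type

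Section 6.3.2 gives no denominator for the percentage and does not say how a participant who has finished sampling enters any of these. Its only rule for values below the limit of quantification (half the limit) covers the individual plots.

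**General rules.** SAP 5.2.1 bases binary summaries on non-missing observations. SAP 5.3 imputes nothing unless Sections 3 or 6 say so, and they do not for by-visit shedding. By contrast, SAP 6.2.1.2 does name a denominator for the FVIII activity categories.

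**Other clearance summaries.** SAP 6.3.2 also reports, per specimen type, peak level, time to peak, the number and percentage reaching three consecutive negatives, and three time-to-clearance measures. SAP 3.3.2 likewise names peak values and time to three consecutive specimens at the limit.

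**The concern.** A participant with no shedding result at a late visit has usually left the sample because he cleared. Missingness is therefore caused by the outcome being summarised. If the by-visit percentage uses observed results only, each participant contributes at most his last three negatives and then drops out of both numerator and denominator. Those remaining at a late visit are selected for still shedding, or for having only just stopped.

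The level displays are affected in the same direction: the absent participants are those whose values would lie below the limit of quantification, so medians and boxes among the rest sit too high. A reader who takes the by-visit row or the median curve as a picture of shedding over time in the dosed population would conclude that clearance is slower and late levels higher than they are, and late points may rest on very few people.

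**Working it through.** The documents state no shedding figure, so there is none to reproduce. The check asks what the planned percentage would show if the true clearance curve were known.

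**Inputs**
- Stopping after three consecutive negatives, weekly collection, two-weekly after Week 20: Protocol 1.3 and 8.5.1.
- Observed-data denominator: inferred from SAP 5.2.1 and 5.3.
- About 70 participants, for scale only: Protocol synopsis.
- Assumption, not in the documents: a constant weekly clearance probability h of 5, 10 or 20%, with no relapse.

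**Formulas.** Let S(t) = (1−h)^t be the proportion not yet cleared at week t.
- True clearance: 1 − S(t).
- With weekly sampling, those still sampled at week t are those not cleared by week t−3, so the proportion sampled is S(t−3).
- Percentage negative among those sampled: 1 − S(t)/S(t−3) = 1 − (1−h)^3.

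**Week 12, weekly sampling**

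| h | True clearance, 1−(1−h)^12 | Negative among sampled, 1−(1−h)^3 | Still sampled, (1−h)^9 |
|---|---|---|---|
| 5% | 1−0.540 = 46% | 1−0.857 = 14% | 63% |
| 10% | 1−0.282 = 72% | 1−0.729 = 27% | 39% |
| 20% | 1−0.069 = 93% | 1−0.512 = 49% | 13% |

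**Week 34, two-weekly after Week 20.** Three negatives now span Weeks 28, 30 and 32, so those sampled at Week 34 are those not cleared by Week 28. The percentage negative is 1 − S(34)/S(28) = 1 − (1−h)^6.

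| h | True clearance, 1−(1−h)^34 | Negative among sampled, 1−(1−h)^6 | Still sampled, (1−h)^28 |
|---|---|---|---|
| 5% | 82.5% | 26.5% | 23.8% |
| 10% | 97.2% | 46.9% | 5.2% |

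**Dependence on the assumed shape.** Results at Week 20 with weekly sampling and median clearance 8 weeks (200,000 simulated participants per row; the first row also follows from the closed form):

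| Scenario | True clearance | Negative among sampled | Still sampled, of 70 |
|---|---|---|---|
| Constant hazard | 82.3% | 22.9% | 16 |
| Weibull, shape 1.5 | 93.6% | 44.4% | 8 |
| Weibull, shape 2.5 | 99.9% | 89.7% | under 1 |
| Lognormal, SD 0.7 | 90.4% | 32.2% | 10 |
| Lognormal, SD 0.4 | 98.9% | 63.2% | 2 |
| Constant hazard, 10% false-positive results | 82.4% | 25.2% | 17 |
| Constant hazard, stopping delayed 3 weeks | 82.2% | 40.3% | 21 |

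With a Weibull shape of 0.7 the observed percentage falls from 23.5% at Week 4 to 10.7% at Week 40, while true clearance rises from 35% to 88%. Once participants begin to stop, the by-visit figure is too low in every scenario, but its size and shape vary widely.

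**The other possible denominator.** If all dosed participants were the denominator and stopped participants were not counted as negative, the percentage would be S(t−3) − S(t). With constant hazard and median 8 weeks this is 21.0% at Week 4, 5.2% at Week 20 and 0.9% at Week 40. Neither reading gives a clearance rate.

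**Check of the repair.** Take h = 10% at Week 12. Those already cleared and stopped are 61.3%; those sampled and negative are 38.7% × 27.1% = 10.5%. The sum is 71.8%, the true value of 1−0.2824.

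**The case against.** The strongest reply is that clearance is reported properly elsewhere. The count with three consecutive negatives and the time-to-clearance summaries do not depend on who is still sampled at a visit, and individual plots are planned. The by-visit row is an addition to these. Shedding is tertiary/exploratory, nothing is tested, and by-visit n is planned, so shrinking numbers will be visible. All of this stands, and it sets the severity. It does not cure the display: the count has no time axis, and SAP 6.3.2 gives no Kaplan-Meier method or censoring rule for the times. Among the planned group displays by visit, every one is affected.

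Three stronger readings are tempting but not supported:
- That the SAP states an observed-only denominator. It does not; this is inferred from the general rules, and 6.3.2 is silent.
- That the by-visit percentage will look flat. That follows only from a constant clearance hazard; it may also rise, fall, or peak and then fall.
- That these are the main shedding display, so that clearance is hidden overall. SAP 3.3.2 and 6.3.2 put peak and time-to-clearance summaries alongside or ahead of them.

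A simple carry-forward over all dosed participants would also be wrong. Postinfusion PBMC collection starts only at Week 20. Participants unable to give semen may stop trying under conditions in Protocol 8.5.1 and never reach three semen negatives. Some visits have no scheduled collection, and a later positive result must not be overwritten. The fix has to allow for these.

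**Conclusion.** The point holds for the by-visit displays. Collection ends because of the outcome, SAP 6.3.2 has no rule for participants who have finished, and the general rules lead to displays of slow clearers at later visits. Clearance is then understated and vector levels overstated. Under the stated assumptions the gap at Week 12 is about 32, 45 and 44 percentage points (46−14, 72−27, 93−49). At Week 34 with two-weekly sampling it is about 56 and 50 points (82.5−26.5, 97.2−46.9). The direction was the same in every scenario tried; the size rests on a clearance distribution that the documents do not give, on the inferred denominator, and on no relapse. The overstatement of levels follows from the selection and was not quantified. No hypothesis test is touched. This is a cheap improvement of minor severity.

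**What to change.** In SAP 6.3.2:

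1. **By-visit percentage.** Count a participant who has met three consecutive negatives in a specimen type as below the limit of quantification at later collection timepoints while he remains in follow-up, unless a later positive is observed. The denominator is participants with a result at that timepoint plus those already cleared. Start postinfusion PBMC summaries at Week 20. Leave participants who could not provide semen out of the semen denominator.
2. **Alternative to item 1.** Add a cumulative-clearance (Kaplan-Meier) curve per specimen type, with censoring at the last sample.
3. **Level displays.** Keep the by-visit median and box plots on observed data. Label them as participants still being sampled, print the number actually sampled under each timepoint, and state how values below the limit enter them.

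The cost is a little programming on data already collected. The percentage then assumes that a cleared specimen type stays cleared, which the protocol's stopping rule already assumes.

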6.3.3. Pharmacodynamics: FVIII antigen levels and von Willebrand factor

The number of participants (n), mean, median, standard deviation, Q1, Q3, min and max by study visit will be provided in the summary tables for FVIII antigen levels and for von Willebrand factor as specified in [Section 3.3.3](#).

6.3.4. Joint Health Assessments

6.3.4.1. Target Joints

Assessment for target joints (hip, elbow, wrist, shoulder, knee, and ankle) will be performed at Screening as part of hemophilia history. A target joint is defined as a major joint (e.g., hip, elbow, wrist, shoulder, knee, and ankle) into which repeated bleeds occur (3 or more spontaneous bleeds into a single joint within a consecutive 6-month period). A target joint is considered resolved when there are ≤ 2 bleeds into the joint within a 12-month period.

Number and percentage of participants with 0, 1, 2 or ≥ 3 target joints at baseline, during the first 15 months post PF-07055480 infusion, and by cumulative follow-up intervals will be summarized, respectively. Number and percentage of participants who have 0, 1, 2 or ≥ 3 baseline target joints resolved during the first 15 months post PF-07055480 infusion, and by cumulative follow-up interval will be summarized. Similarly, number and percentage of participants who developed new target joints (1, 2 or ≥ 3 target joints) during the first 15 months post PF-07055480 infusion, and by cumulative follow-up interval will be summarized. The number and location of target joints at baseline and post PF-07055480 infusion will be provided in a data listing. The summary will be based on the ‘Dosed’ population.

6.3.4.2. X-ray Assessments to Evaluate Joints

Total score, scores at specific joints, and scores at target joints based on the Pettersson scale, as well as the change from baseline will be summarized. The observed values will be compared to the corresponding baseline using paired t-test.

The number of participants with non-missing observations (n), mean, median, standard deviation, Q1, Q3, min, max, and the 95% CI of mean for the observed value and change from baseline, as well as the p-value from the paired t-test for change from baseline, will be provided by visit based on the ‘Joint X-Ray Substudy’ population.

6.3.4.3. Ultrasound Substudy

A subset of participants (n~20) will undergo ultrasound exams (at Screening, Week 24, and Week 52) to assess damage within joints by evaluating soft-tissue changes and osteochondral changes. The ultrasound scanning protocol will include acquisition of knees, elbows, and ankles.

Joint images will be reviewed following the extended ultrasound scale (i.e., HEAD-US) with a final score combining soft tissue and osteochondral subscores and compared to baseline (at Screening period). Total score for each joint will be summarized by visit with descriptive statistics and 95% CI for mean observed value and mean change from baseline.

In addition, demographic and baseline characteristics, AEs, disposition, and FVIII activity level data collected for the participants in this substudy will be summarized.

Summary tables will be generated for the participants in ‘Evaluable’ population in the ‘Ultrasound Substudy’ population.

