9.3. Populations for Analyses

For purposes of analysis, the following populations are defined:

Population	Description
Enrolled	All participants who sign the ICF and meet all inclusion/exclusion criteria.
Dosed/Safety	All participants enrolled in the study and who receive the study intervention.
Evaluable	All participants enrolled in the study and who receive the study intervention and have no significant interruption of efficacy measurement and no major protocol deviation.
Efficacy	All participants in the “Dosed” population who have completed at least 6 months in the lead-in study and at least 15 months of follow-up or discontinued from the study C3731003 prior to the data cutoff for reporting.

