4. ANALYSIS SETS (POPULATIONS FOR ANALYSIS)

For purposes of analysis, the following populations are defined:

Population	Description	Applicable Analysis (for additional information refer to Section 6)
Enrolled	All participants who sign the informed consent form (ICF) and meet all inclusion/exclusion criteria.	Disposition events summary
Dosed/Safety	All participants enrolled in the study and who receive the study intervention.	Demographic and baseline characteristics, hemophilia history, medical history, safety, nAbs, ADA, FVIII antigen, von Willebrand factor, vector shedding assessments, joint health assessments, efficacy sensitivity/supplementary analyses, PRO analyses, and coagulation activation tests.
Evaluable	
All participants enrolled in the study and who receive the study intervention and have no significant interruption of efficacy measurement.
 
The ‘Evaluable’ analysis population will include participants who receive the study intervention (full dose of infusion) and exclude participants with significant interruption of efficacy measurement. The significant interruption would occur if the participant discontinues from the study, is lost to follow-up, has significant
	Efficacy sensitivity/supplementary analyses

Population	Description	Applicable Analysis (for additional information refer to Section 6)
	interruption in data collection, or has a major protocol deviation.	
Efficacy	All participants in the 'Dosed' population who have completed at least 6 months of follow up in the lead-in study and at least 15 months of follow up or discontinued from the study C3731003 prior to the data cutoff for reporting.	Main analysis population for efficacy
Ultrasound Substudy	All participants who sign the additional ICF for the ultrasound substudy and meet all inclusion/exclusion criteria, and the participant's joint ultrasound have been reviewed following the extended ultrasound scale at baseline, and any data post-baseline.	HEAD-US ultrasound scale - total score and subscores, demographic and baseline characteristics, AEs, disposition, and FVIII activity level data.
Vector Shedding Substudy	All participants who sign the additional ICF for the Vector Shedding substudy and meet all inclusion/exclusion criteria, and who provide any additional vector shedding data for analysis.	Shedding vector levels in PBMC, saliva, urine, semen, and plasma; demographic and baseline characteristics, AEs, disposition, and FVIII activity level data.

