Joint status as assessed by X-ray in Pettersson scale: change from baseline in total score, scores at specific joints, and scores at	Final analysis: Tertiary/Exploratory	Joint x-ray substudy	No imputation for missing data.	Descriptive summary, 95% CI of mean for the observed value and

Endpoint	Analysis Type	Population	Data Inclusion and Rules for Handling Intercurrent Events and Missing Data	Analysis
target joints at Week 156 (Year 3) and Week 260 (Year 5 or Early Discontinuation Visit)				change from baseline, and p-value from the paired t-test.
Joint status as assessed by ultrasound based on HEAD-US scoring at Week 24, Week 52 or Early Discontinuation Visit	Primary analysis: Tertiary/Exploratory	Evaluable population in the ultrasound substudy	No imputation for missing data.	Counts and percent for individual items. Total score for each joint will be summarized by visit with descriptive statistics and 95% CI of mean for the observed value and change from baseline.
PGIS and PGIC by visit	Primary analysis and Final analysis: Tertiary/Exploratory	Dosed	No imputation for missing data.	Counts and percent.
HLIQ by visit	Primary analysis and Final analysis: Tertiary/Exploratory	Dosed	No imputation for missing data.	Counts and percent by response to individual items.
Change from baseline in EQ-5D-5L Index score and VAS score by visit	Primary analysis and Final analysis: Tertiary/Exploratory	Dosed	No imputation for missing data.	Descriptive summary, 95% CI of mean for the observed value and change from baseline, and p-value from the paired t-test.

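### SAP 6.3.4.3 puts the ultrasound-substudy tables on the Evaluable population, which excludes dropouts, while SAP 4 assigns the same tables to the Ultrasound Substudy population

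*SAP*

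**What the plan says.** SAP 6.3.4.3 describes the HEAD-US summaries and adds that "demographic and baseline characteristics, AEs, disposition, and FVIII activity level data collected for the participants in this substudy will be summarized". Its last sentence sets the population: "Summary tables will be generated for the participants in ‘Evaluable’ population in the ‘Ultrasound Substudy’ population".

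SAP 4 defines Evaluable as participants who received the full dose, and says it will "exclude participants with significant interruption of efficacy measurement". It explains the term: "The significant interruption would occur if the participant discontinues from the study, is lost to follow-up", or if data collection is significantly interrupted or there is a major deviation. Protocol 9.3 is less explicit. It asks that participants "have no significant interruption of efficacy measurement and no major protocol deviation", and does not name discontinuation.

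The Ultrasound Substudy row of the same SAP 4 table lists as its applicable analyses "HEAD-US ultrasound scale - total score and subscores, demographic and baseline characteristics, AEs, disposition, and FVIII activity level data", with no Evaluable filter. The Evaluable row is given only efficacy sensitivity and supplementary analyses.

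Appendix 2 has one ultrasound row, for HEAD-US joint status. Its population is "Evaluable population in the ultrasound substudy", and its timepoints include the Early Discontinuation Visit, as does the scan schedule in SAP 3.3.4.1. SAP 6.6 puts all safety analyses, AEs included, on the Safety population.

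**The concern.** A disposition table exists to show who left. Run on a set from which leavers have been removed, it cannot do so. An AE table on that set omits the events of participants who left, and a joint-score summary becomes a summary of those who stayed.

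The plan also names a scan at early discontinuation and then tabulates HEAD-US in a population that cannot contain a discontinued participant.

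The practical stake is that two programmers could work from the same SAP, one from Section 4 and one from 6.3.4.3, and produce different substudy tables. If those who leave tend to have poorer joint outcomes, the 6.3.4.3 version would also look too favourable.

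**Working it through.** The documents give no sample size calculation, power or dropout rate for this substudy, so there is no planned figure to reproduce. The check is on the wording, with an illustration of size.

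**Which population each place names**

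| Output | SAP 4 | SAP 6.3.4.3 | Appendix 2 | SAP 6.6 |
|---|---|---|---|---|
| HEAD-US | Ultrasound Substudy | Evaluable within substudy | Evaluable within substudy | – |
| Substudy AEs | Ultrasound Substudy | Evaluable within substudy | no row | Safety |
| Substudy disposition | Ultrasound Substudy | Evaluable within substudy | no row | – |
| Demographics, FVIII activity | Ultrasound Substudy | Evaluable within substudy | no substudy row | – |

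The other joint and substudy analyses do not use Evaluable. The X-ray summary uses its own substudy population (SAP 6.3.4.2), vector shedding uses its substudy and Dosed populations (6.3.2), and HJHS uses Dosed (6.2.10).

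**What follows if 6.3.4.3 is applied literally**

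1. The analysed set is the overlap of Evaluable and Ultrasound Substudy.
2. Evaluable contains no one who discontinued, so the substudy disposition table shows 0 study discontinuations whatever happened. This needs no assumption about dropout.
3. Only a discontinued participant can have an Early Discontinuation Visit scan, so no such scan can be tabulated.
4. The exclusion has no time limit and no link to the last scan. Scheduled scanning ends at Week 52, but Appendix 2 places the HEAD-US summary at the primary analysis, when at least 50 participants have reached 15 months. A man with baseline, Week 24 and Week 52 scans who leaves between Week 52 and the cutoff loses all of them: up to 6 joints × 3 timepoints = 18 joint scores.

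**Size, for n = 20**

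Each exclusion removes 1/20 = 5% of the sample. Let d be the proportion of substudy participants who discontinue before the cutoff. The values of d are assumptions. The largest comes from the planning figures of about 70 enrolled to obtain 50 with 15 months of follow-up, 1 − 50/70 = 28.6%, and serves only as an upper bound. Expected exclusions are 20d, and the chance of at least one is 1 − (1 − d)^20.

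| d | Expected excluded | Chance of at least one |
|---|---|---|
| 2% | 0.4 | 33% |
| 5% | 1.0 | 64% |
| 10% | 2.0 | 88% |
| 20% | 4.0 | 99% |
| 28.6% | 5.7 | 99.9% |

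The loss of precision is modest. Confidence-interval width grows by about 1/√(1 − d), which is 1.05 at d = 10% and 1.12 at d = 20%.

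On the Ultrasound Substudy population of SAP 4, no participant with a baseline scan and post-baseline data is removed for discontinuing.

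**The case against.** The strongest reply is that this is a wording conflict with little consequence. Much of that stands, and it rules out several stronger readings that a reader might infer.

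- **That the substudy disposition and AE tables are wrong, with dropout always reported as 0%.** The documents do not settle this. SAP 4 gives the same outputs to the unfiltered population, so the result holds only if 6.3.4.3 prevails.
- **That Appendix 2 confirms the restriction for all substudy tables.** It does so for HEAD-US only. For AEs, disposition, demographics and FVIII activity, the restriction rests on one closing sentence in 6.3.4.3.
- **That safety or disposition information is lost from the trial.** It is not. Whole-study disposition uses the Enrolled population, and the whole-study AE tables use the Safety population, so every substudy participant who leaves appears there.
- **That the HEAD-US change is biased.** This is possible, since SAP 3.2.4 provides for discontinuation due to lack of efficacy. But a participant with a poor response may resume prophylaxis and stay in the study, and resumption is not among the listed reasons for leaving Evaluable. No figure supports a direction or size.

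One may also say that restoring SAP 4's assignment is enough, and that a further set for disposition and AEs is a preference. As a matter of consistency that is right. The Ultrasound Substudy population, however, requires a reviewed baseline scan and post-baseline data, so it can still miss someone who leaves before Week 24. That is the reason for the further suggestion below.

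**Conclusion.** The inconsistency is real and should be resolved before programming. Read literally, 6.3.4.3 makes the substudy disposition table unable to show a study discontinuation, leaves participants who left out of the substudy AE table, and drops HEAD-US scans that the plan itself provides for. The first consequence follows from the definitions alone. The number of participants and scans lost depends on a dropout rate that the documents do not give: an expected 1 to 4 of 20 for assumed rates of 5% to 20%.

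The effect is confined to an exploratory, descriptive substudy of about 20 participants with no hypothesis test. The primary and gatekept conclusions are unaffected. This is a minor point, worth making because the remedy costs almost nothing.

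**What to change.** 1. In SAP 6.3.4.3 and in the HEAD-US row of Appendix 2, replace the Evaluable restriction with the Ultrasound Substudy population as SAP 4 defines it. State that all available scans are used, including any from an Early Discontinuation Visit.
2. Preferably, base the substudy disposition and AE tables on all dosed participants who signed the substudy consent form, and add that set to the SAP 4 table so that someone who leaves before a post-baseline scan is still counted.
3. If an Evaluable version of HEAD-US is wanted, keep it as a labelled sensitivity summary, which fits the use SAP 4 gives to that population.

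The cost is a few lines of SAP wording. No new data, visits or analysis methods are needed.
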